Brief Summary	African-Americans (AAs) have an increased prevalence of both Alzheimer's disease (AD) and vascular risk factors for AD such as diabetes and hypertension when compared to whites. However, in a recent community based study of non-demented elderly, black race was associated with higher amyloid burden after adjusting for vascular risk factors, suggesting the presence of additional physiological differences on AD-risk by race in the early stages of the disease. The purpose of this study is to test whether poor slow wave sleep (SWS) quantity (SWS duration) and quality (slow wave activity, SWA) is one of these physiological factors. To test these hypotheses, we will perform community outreach in barbershops, churches and senior centers in Brooklyn and other NYC boroughs with which we have created substantial ties in recent years. In consultation with community stakeholders, we will recruit 150 cognitively normal AA elderly (age 60-75) and 60 age, sex, BMI, income and education matched non-Hispanic whites from the same geographical areas. We will first perform a medical and cognitive evaluation (Visit 1). Participants will then undergo 2 nights of home sleep monitoring using an unattended device to exclude OSA, followed by 7 days of actigraphy with a sleep log to record sleep duration. Both devices will be returned by mail. Subjects with reported total sleep time (TST) between 5 and 10 hours and absence of moderate to severe OSA will be invited to perform a 2-night nocturnal polysomnography (NPSG) (Nights 1-2) and a PiB-PET MR scan (Visit 2).
Objectives	Objective 1: To test if African ancestry (%AF) is associated with short SWS duration and poor SWA in older AAs. Objective 2: To test the effect of race and its interaction with baseline short SWS duration/poor SWA on longitudinal amyloid deposition. Objective 3: To test the effect of race and baseline poor SWA on cognition. Secondary Objective 2.1: To test whether loss of sleep-dependent spatial navigational memory at baseline is a predictor of cognitive decline.
Methodology	30-36 month longitudinal study
Endpoint	Primary endpoint is longitudinal increase in amyloid deposition
Study Duration	5 years
Participant Duration	30-36 months

CONFIDENTIAL

[figure not shown]
This material is the property of the NYU School of Medicine and Langone Medical Center. Do not disclose or use except as authorized in writing by the study sponsor

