
Population
	
210 cognitively normal elderly (Clinical Dementia Rating [CDR]=0), self-identified as African-American (AA) or non-Hispanic white (NHW), ages 60 to 75 years, with English as their primary language. The reason for only including native English speakers is due to the nature of the study and cognition being one of the outcomes of the study. The reason for including only African American blacks and NHW is the focus of this grant which is on African Americans and their African genetic ancestry and admixture. Based on our preliminary data an existing literature, in order for genetic admixture analyses to be applied rigorously, the control group needs to be of NHW. The definition of NHW are people in the United States who are considered racially white and are not of Hispanophone identity or the Hispanosphere (terms used to refer to Spanish-language speakers and the Spanish-speaking world as compared to for example English-speaking of French-speaking to name a few). Other non-English non-Hispanic white ethnicities will not be invited to participate due to the lack of adequate neuropsychological tools and testers proficient in other native European languages and the confounding effects of immigration. These NHW participants will be located within the same zip codes as the AAs.

Study Sites
	
NYU locations: the Center for Brain Health (CBH) at NYULMC, the Center for Biomedical Imaging (CBI), NYU Langone Health, Department of Radiology, [name]
 
External Site: the Mount Sinai Integrative Sleep Center (MSISC) (New York, NY)

Number of participants
	
210 participants expected to be enrolled with 150 cognitively normal African-American elderly and 60 non-Hispanic white.

Statistical Analysis
	
We will incorporate standard techniques such as omnibus tests and appropriate adjustments to significance (α) levels (e.g., Bonferroni correction) for post-hoc contrasts to control for multiple comparisons. Both selection and attrition biases might occur. Appropriate techniques (e.g., Heckman 2-stage approach (GEE Probit Model) and Monte Carlo (EM algorithm) will be used to address biases or missing data. Since only two time points will be analyzed, we will use linear regression models with the annual rate of amyloid change as dependent variable. Significance will be defined by $p < .05$ where p will be Bonferroni corrected when testing post-hoc contrasts.

CONFIDENTIAL

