2.2 Rationale

Primary Aims. To examine: *i*) whether African Ancestry (%AF) is associated with decreased SWS duration and SWA; *ii*) the effects of race on longitudinal amyloid build-up and its interaction with baseline SWS duration and SWA in cognitively normal elderly; *iii*) the effects of race and its interaction with baseline SWA on longitudinal changes in global cognition, memory, executive function and a spatial navigational memory task. **Exploratory aim.** We will test whether loss of sleep-dependent spatial navigational memory at baseline is a predictor of cognitive decline at follow-up.

Rationale for ethnicity/nativity and clinical groups selection:

Multiethnic cohort studies provide better information about disease causation but they are expensive to design. We will focus on 150 African-American (AA) blacks since African or Caribbean-born are not equally admixed and inclusion of more ethnic groups would result in loss of power for Aim 1 and need for great increases in sample size. As a comparison group, we will include 60 matched non-Hispanic whites. Race will be represented both as binary (self-identified AA vs. self-identified white) and numeric (% of African ancestry). Irregular sleep-wake rhythms and extreme sleep durations may also increase AD risk⁶⁸⁻⁷⁰. The study will not formally test these sleep disorders, as these subjects are hard to recruit in community-based

CONFIDENTIAL

studies (often reluctant to participate in studies that monitor sleep) and the focus is on SWS. Insomnia will be allowed as long as total sleep time (TST) is between 5-9 hours based on actigraphy recordings and sleep logs performed at home.

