3.1 Primary Objective

Aim 1 will test if African ancestry (%AF) is associated with short SWS duration and poor SWA in older AAs. **Challenge:** AAs consistently spend less time in SWS than whites²³⁻³². Although SWS shows significant heritability, social stressors may moderate these differences. **Approach:** test whether %AF⁴⁰ is associated with SWS characteristics after controlling for psychosocial factors (*e.g.* stress related to ethnicity). **Outcome:** positive results would suggest that racial differences in SWS have genetic underpinnings.

Aim 2 will test the effect of race and its interaction with baseline short SWS duration/poor SWA on longitudinal amyloid deposition. **Challenge:** AAs spend less time in SWS²³⁻³², a sleep stage important for A β dynamics⁴¹⁻⁴³ that may confer protection against amyloid deposition⁴⁴. **Approach:** assess how race is associated with longitudinal PiB uptake and its interaction with short SWS duration and poor SWA, after controlling for: 1) medial prefrontal (mPFC) atrophy, TST, AHI4% and cerebrovascular damage (measured as white matter lesion [WML] volume and abnormal diffusion kurtosis imaging [DKI] indices); and, 2) psychosocial factors, health care behaviors and medical morbidity. **Outcome:** reduced SWS/SWA would become a novel risk factor for AD in African Americans (AAs).

Aim 3 will test the effect of race and baseline poor SWA on cognition. **Challenge:** race and poor sleep have been associated with cognitive impairment. However, most studies are confounded by the inclusion of OSA patients, subjective measurements of sleep, lack of valid cognitive assessments for AAs and inadequate enrollment of minorities. **Approach:** we will test for the association between race and longitudinal changes in global cognition, memory, executive function and a sleep-dependent spatial navigational memory task. In addition, we will test their interaction with baseline SWA, using a similar approach as in Aim 2. **Outcome:** positive results would emphasize the importance of health messages promoting good sleep hygiene among AA elderly.

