9.1 Study Hypotheses

1. Hypothesis 1.1: poor SWS characteristics (short SWS duration, low %SWS, low relative SWA, low SWS continuity and high AI) at baseline will be associated with high %AF. Hypothesis 1.2: psychosocial factors (*e.g.* perceived discrimination) will partially moderate the above relationships.
2. Hypothesis 2.1: race will be associated with longitudinal increases in the annual rate of AD_{PiB}mask change. Hypothesis 2.2: the effect of race in terms of longitudinal increases in AD_{PiB}mask will be partially explained by poor relative SWA at baseline.
3. Hypothesis 3.1: race will be associated with longitudinal changes in global cognition, memory, executive function and sleep-dependent spatial navigational memory. Hypothesis 3.2: the association of race in terms of cognitive decline will be partially explained by poor relative SWA at baseline. Exploratory Hypothesis: absence of improvement in sleep dependent memory consolidation at baseline will be associated with longitudinal decreases in global cognition, memory and executive function.

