9.2 Sample Size Determination

Power was assessed under the assumption that dropout replacement will allow complete data to be acquired from 200 subjects. Based on the existing literature²³⁻³², the coefficient of variation (CV) of SWS duration is anticipated to be as high as 90% among AA and 40% among whites. Baseline data from 150 AA and 60 whites will therefore provide 80% power at the 5% significance level to detect a mean SWS duration among whites that is at least 28% higher than among AA. Based on PD4, the CV of PiB uptake at baseline is anticipated to be as high as 35% among AA and 25% among whites, providing 80(90)% power at the 5% significance level to detect a mean PiB uptake among AAs that is at least 13%(15%) higher than in whites. For Aim 1, the study will have 80% power at the 5% significance level to detect correlations of magnitude $|r|=0.20$ (the study from Halder et al³⁹ showed an R^2 of 11, implying an even greater correlation of 0.33 can be expected in our study). The multivariable regression analysis will have 80% power to detect SWS characteristics that can explain 3% of the variance in the longitudinal change in AD_{PiB}mask (Aim 2) or cognition (Aim 3) after adjusting for covariates that together explain at least 25% of the variance in AD_{PiB}mask/cognition. The detectable effect of 3% variance explained, implies the study can detect partial correlations of magnitude 0.1 between SWS and the outcomes adjusted for the cofactors. It is noted that the power of the multivariable analyses will improve if the covariates explain >25% of the variance. The study will have 80% power to detect sleep measures that explain 10% of the variance in the AD_{PiB}mask ratio even if the covariates explain a negligible percentage of the variance.

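### Aim 1: the 80% power at |r| = 0.20 fits about 200 participants, but the objective concerns the 150 African Americans, where power is about 69%, and section 9.3 names no analysis set for H1.1

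*Combined protocol and SAP*

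**What the plan says.** The power statement for Aim 1 in section 9.2 reads "For Aim 1, the study will have 80% power at the 5% significance level to detect correlations of magnitude" |r| = 0.20. It gives no sample size of its own. The section opens with a general basis: "Power was assessed under the assumption that dropout replacement will allow complete data to be acquired from 200 subjects". The comparison of mean slow wave sleep (SWS) duration that follows uses a different one: "Baseline data from 150 AA and 60 whites will therefore provide 80% power at the 5% significance level". Section 9.2 adds that a cited ancestry study implies a correlation of 0.33.

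The objective is narrower than 200 subjects. The Protocol Summary gives Objective 1 as "To test if African ancestry (%AF) is associated with short SWS duration and poor SWA in older AAs", and section 3.1 repeats it: "Aim 1 will test if African ancestry (%AF) is associated with short SWS duration and poor SWA in older AAs". The plan has 150 African Americans (AAs) and 60 non-Hispanic whites (NHW).

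Other places carry no such restriction:

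- Section 2.2 asks only "whether African Ancestry (%AF) is associated with decreased SWS duration and SWA".
- Hypothesis 1.1 in section 9.1 ends "low SWS continuity and high AI) at baseline will be associated with high %AF".
- The H1.1 model in section 9.3 regresses each SWS characteristic on %AF with seven covariates (age, sex, BMI and four sleep measures) and names no analysis set.
- The Population entry of the Protocol Summary says that "in order for genetic admixture analyses to be applied rigorously, the control group needs to be of NHW", which suggests some role for the white group.
- Separate AA and white analyses appear in 9.3 only among the post-hoc analyses, and not specifically for Aim 1.

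**The concern.** A correlation within 150 people is estimated less precisely than one within 200, so a power figure for the larger number overstates what the smaller group can show. If Aim 1 is the within-AA question its objective describes, 9.2 promises more than the design delivers.

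The missing analysis set adds to this. H1.1 could be fitted in the AAs alone, which estimates an ancestry gradient within that group. It could also be fitted in everyone, and the %AF slope would then mostly separate AAs from whites. Section 3.1 says a positive Aim 1 result would point to a genetic basis for racial differences in SWS. A pooled slope, from a model with neither a race term nor a psychosocial term, cannot carry that conclusion alone, because any social difference between the groups enters it too.

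**Working it through.** **Inputs.** From 9.2: |r| = 0.20, 5% level, 80% power, 200 subjects with complete data, 150 AA and 60 white, expected r = 0.33. From 9.3: seven H1.1 covariates. Sidedness is not stated. Aim 1 uses baseline data, so follow-up dropout does not reduce the 150.

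**Formula.** Fisher z, two-sided 5%: power = Φ(atanh(r)·√(n − 3 − k) − 1.96), where k is the number of covariates. atanh(0.20) = 0.2027.

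**The plan's own figure.**

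- Required n = ((1.960 + 0.842)/0.2027)² + 3, which rounds up to 194.
- n = 200: 0.2027 × √197 = 2.845; Φ(0.885) = 81.2% (79.8% with k = 7).
- n = 210: 83.1%.

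So 80% agrees with the 200-subject basis.

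**The population in the objective, n = 150.**

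- 0.2027 × √147 = 2.458; Φ(0.498) = 69.1%. The chance of a miss is 30.9%.
- With k = 7: 67.0%.
- Cross-checks without covariates: simulation of the exact test 69.4%, noncentral F 70.0%.
- Smallest |r| with 80% power: tanh(2.80/√147) = 0.227; with k = 7, tanh(2.80/√140) = 0.232.
- At r = 0.33: 98.6% (98.2% with k = 7).

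**Sidedness.** One-sided 5% at n = 150 gives Φ(2.458 − 1.645) = 79.2%, which would also look like 80%. The neighbouring claims in 9.2 show which convention was used. With 150 AA and 60 white, each SD equal to CV times the group's own mean, and a normal approximation:

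| Claim in 9.2 | Stated power | Two-sided | One-sided |
|---|---|---|---|
| SWS 28% higher in whites | 80% | 80.9% | 88.3% |
| PiB 13% higher in AAs | 80% | 81.3% | 88.5% |
| PiB 15% higher in AAs | 90% | 90.3% | 94.6% |

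The first row, for example: SE = √(0.90²/150 + (0.40 × 1.28)²/60) = 0.0988, and 0.28/0.0988 = 2.83. All three claims match two-sided and none matches one-sided. The Aim 1 effect is also written as an absolute value.

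**What a pooled model would estimate.** The documents give no ancestry distribution, so this step is an assumption: AA mean %AF 75 to 80 with SD 10 to 18, whites mean 1 and SD 1. The correlation of %AF with binary race is √(B/(B + W)), with B = pq(m_A − m_W)², W = p·s_A² + q·s_W², p = 150/210 and q = 60/210. With mean 75 and SD 18, B = 0.2041 × 74² = 1117.6 and W = 231.7, giving 0.910. With mean 80 and SD 10 it is 0.973. Over this range %AF is close to a stand-in for self-identified race.

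**The case against.** The strongest reply is that nothing is miscalculated. Section 9.2 declares 200 subjects, speaks of the study as a whole, and its 80% reproduces. Sections 2.2, 9.1 and 9.3 carry no AA restriction, so a pooled H1.1 may be what was meant. That stands as far as the arithmetic goes, and the defect is better called an inconsistency than a miscalculation. It does not remove the problem, because a pooled model saves the number only by leaving the stated objective. Two other places favour the within-AA reading: section 2.2 justifies concentrating on 150 AAs partly by the power for Aim 1, and the study behind the 0.33 benchmark is, by its title in the reference list, about older African Americans.

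A second reply is that H1.1 is directional and a one-sided test at n = 150 gives 79.2%. This is possible, since sidedness is unstated, but the neighbouring claims point the other way.

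A third is that subtracting degrees of freedom gives the covariates no credit for the variance they explain. Suppose 0.20 is the marginal correlation and the covariates are unrelated to %AF. The partial correlation is then 0.20/√(1 − R²), and with n = 150 and k = 7 power is about 72% at R² = 10%, 79.5% at 25% and 82% at 30%. The 69% therefore depends on reading 0.20 as the correlation actually tested. But 9.2 uses 25% only for Aims 2 and 3 and gives no share for Aim 1, and covariates related to %AF would change the result.

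It is also fair to say that H1.2 does bring in psychosocial factors. It does so as an interaction model for the best SWS measure, not as adjustment in H1.1.

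**Conclusion.** The concern holds. For the 150 African Americans named in the Aim 1 objective, power at |r| = 0.20 is about 69%, some 11 points below the stated 80%, and the correlation detectable with 80% power is about 0.23. This rests on a two-sided 5% test and on 0.20 being the correlation tested. The missing H1.1 analysis set is a separate gap that needs no calculation to see; that a pooled slope would largely be a race contrast rests on the assumed ancestry distributions.

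The consequence is moderate. If the expected 0.33 is right, the AA-only analysis has 98 to 99% power, and the primary endpoint, longitudinal amyloid, is not touched. It should be fixed because Aim 1 could otherwise be answered by either of two models, only one of which matches its objective.

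**What to change.** In section 9.2, give the Aim 1 power for 150 African Americans: 80% for |r| of about 0.23, and about 69% at |r| = 0.20, two-sided 5%.

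In section 9.3, state that the H1.1 models addressing the objective are fitted in the African American participants, and explain what part the white group plays in the admixture analyses that the Protocol Summary mentions. Align sections 2.2 and 9.1 with this. If a pooled model is also wanted, give it its own power figure, report it separately, and do not rest a genetic interpretation on it alone.

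The cost is one restated figure and one or two sentences on the analysis set, with matching wording in 2.2 and 9.1. The study does not need resizing, and no additional data are required.

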9.3 Statistical Methods

General considerations: we will incorporate standard techniques such as omnibus tests and appropriate adjustments to significance (α) levels (*e.g.*, Bonferroni correction) for *post-hoc* contrasts to control for multiple comparisons. Both selection and attrition biases might occur. Appropriate techniques (*e.g.*, Heckman 2-stage approach (GEE Probit Model)^{254;255} and Monte Carlo (EM algorithm)²⁵⁶ will be used to address biases or missing data. Attributes of those who withdrew to follow-up will be contrasted with completers to determine sources of attrition biases. Since only two time points will be analyzed, we will use linear regression models with the annual rate of amyloid change as dependent variable. Significance will be defined by $p < .05$ where p will be Bonferroni corrected when testing *post-hoc* contrasts.

- **Hypothesis (1)**: H1.1) for %AF associations, linear regression models, with each of SWS characteristics as the dependent variable, will be regressed on %AF controlling for age, sex, BMI, AHI, TST, sleep efficiency and WASO. H1.2) This model will test interaction by including the best SWS predictor as dependent variable, the psychosocial factor as a classification factor, %AF and the term created as the cross product of psychosocial factors and %AF.
- **Hypothesis 2-3 (H2-3)**: First we will calculate the associations between race and AD_{PiB}mask represented both as binary (AA *vs.* white) and numeric (%AF). Further analyses will use the representation (s) of race significantly associated with amyloid burden. Second, we will use hierarchical

CONFIDENTIAL

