linear regression, with rate of change of AD_{PiB}mask as the dependent variable and race as independent, adjusting for the matching factors: age, sex, BMI, education and annual income (block 1); ApoE4 and ABCA7 (block 2); DWML volumes, DKI indices and mPFC volume (block 3); and SWS characteristic (*e.g.* relative SWA) (block 4). Other covariates (*e.g.*, psychosocial) will be included in the final models if significantly different between AAs and whites as indicated by unequal variance t tests. Although we anticipate that relative SWA will be the best predictor of longitudinal change in AD_{PiB}mask, the best fitting model will be then replicated with each of the other SWS characteristics not listed before. On a final step, we will test whether the effect of SWS on amyloid deposition is different (*i.e.*, stronger) among AAs. The model would include AD_{PiB}mask change, the binary indicator of race (AA=1 *vs.* white=0) and SWA as described in H1.2. If the interaction is significant, it will imply that the effect of SWA on amyloid varies as a function of race. The sign of the estimated coefficient for this term would indicate whether SWA has a significantly stronger or weaker effect among AA. Exploratory Hypothesis: cognitive z-score change in subjects that show improvement in maze CT will be compared with those that don't show improvement using ANCOVA controlling for age, sex, BMI, race, education and ApoE4 status.

- **Post-hoc analyses**: a subset of *post-hoc* analyses will be performed by controlling by PiB levels at baseline and by splitting the sample into PiB+ and PiB- at baseline and performing a separate analysis for each subset. Stratified analyses will also be performed for men and women, as well as for AAs and whites. In addition, we will formally test the impact of PiB status (defined as PiB SUVR \geq 1.4) on the association of sleep measures with longitudinal increases in AD_{PiB}mask. Although we do not anticipate that sleep or SWS characteristics will change over the follow-up period, *post-hoc* analyses will be performed by assessing longitudinal changes in the sleep measures as correlates and predictors of longitudinal changes in the outcomes measures, using paired sample t-tests to assess the change in outcomes and sleep.

10 Source Documents and Access to Source Data/Documents

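### Section 9.2 turns a detectable effect of 3% of variance into a partial correlation of 0.1; the correct value is 0.20, and power at 0.1 is about 29%

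*Combined protocol and SAP*

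**What the plan says.** All the power statements are in section 9.2 of the combined protocol and SAP. The sample size basis is: "Power was assessed under the assumption that dropout replacement will allow complete data to be acquired from 200 subjects".

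For the regression models of Aims 2 and 3 the section claims "80% power to detect SWS characteristics that can explain 3% of the variance in the longitudinal change" in the amyloid index or in cognition, after adjustment for "covariates that together explain at least 25% of the variance". The following sentence restates that effect as a correlation: "The detectable effect of 3% variance explained, implies the study can detect partial correlations of magnitude 0.1", adjusted for the cofactors.

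Two neighbouring statements are relevant. For Aim 1 the section gives |r| = 0.20 as detectable with 80% power at the 5% level. It closes by claiming "80% power to detect sleep measures that explain 10% of the variance" in the amyloid ratio even if the covariates explain almost nothing.

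Section 9.3 sets significance at p < .05 without saying whether tests are one- or two-sided. It enters an SWS characteristic, such as relative slow wave activity, as block 4 of a hierarchical regression, after which "the best fitting model will be then replicated with each of the other SWS characteristics not listed before".

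**The concern.** The 3% figure and the partial correlation of 0.1 are offered as the same detectable effect on two scales, but they are different effects. A squared partial correlation is the added variance divided by the variance the covariates leave unexplained, so it cannot be smaller than the added variance itself. With 3% added, the partial correlation cannot be below √0.03 = 0.17.

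The sentence describes sensitivity for the sleep effect on change in amyloid, the primary endpoint (Aim 2), and on cognition (Aim 3). Relative slow wave activity is the explanatory variable in hypotheses 2.2 and 3.2. If its coefficient is not significant, a reader who relies on the 0.1 would conclude that correlations of that size had been looked for with adequate power. They would not have been.

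**Working it through.** **Inputs.** From section 9.2: n = 200 complete participants, 80% power, added variance ΔR² = 0.03, covariate R² = 0.25. The 5% level comes from section 9.3 and the neighbouring statements in 9.2. Assumptions: one tested degree of freedom, because one SWS characteristic enters at a time; two-sided testing, with one-sided also shown because sidedness is not stated; and 0 to 20 covariates, because the plan gives no count.

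**Step 1: reproduce the plan's 80%.**

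- Effect size: f² = ΔR² / (1 − R² − ΔR²) = 0.03 / 0.72 = 0.0417.
- Noncentral F with 1 numerator df and noncentrality f² × n = 0.0417 × 200 = 8.33 gives power of 81.9%, almost unchanged by the number of covariates.
- Noncentrality conventions that charge for the covariates give 78–81% with 5 to 15 covariates.
- Simulations of a regression with 11 covariates (R² = 0.25, n = 200) gave 78–80%.
- Solving for exactly 80% power (noncentrality f² × n) gives an added variance of 2.86%, which rounds to 3%.

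The 3% statement is right.

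**Step 2: convert 3% to a partial correlation.**

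- Partial r = √(ΔR² / (1 − R²)) = √(0.03 / 0.75) = √0.04 = **0.20**.
- The partial r with exactly 80% power at n = 200 is 0.195, in agreement.

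**Step 3: look for a reading that gives 0.1.**

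| Reading of the 3% | Correlation |
|---|---|
| Added variance, covariates explain 25% | 0.200 |
| Added variance, covariates explain 30% | 0.207 |
| Added variance, covariates explain 40% | 0.224 |
| Added variance, covariates explain 50% | 0.245 |
| Squared semipartial, or squared partial directly | 0.173 |

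Covariates explaining more than 25% push the value up, not down. None of the readings gives 0.1.

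**Step 4: what a partial correlation of 0.1 would mean.**

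- Added variance: 0.1² × 0.75 = 0.0075, or 0.75%, which is a quarter of 3%.
- f² = 0.01 / 0.99 = 0.0101; noncentrality at n = 200 is 2.02.
- Power is 29.3% two-sided. Conventions that charge for up to 15 covariates give 27–29%, and simulation gave 27%. One-sided power is about 41%.
- With n = 190 or 210, two-sided power is 28.1% or 30.5%.
- Sample size for 80% by Fisher z, two-sided: ((1.960 + 0.842) / 0.1003)² + 3 ≈ 783; noncentral F gives 779. One-sided: ((1.645 + 0.842) / 0.1003)² + 3 ≈ 617.

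**Step 5: the closing 10% sentence (secondary).** With covariate R² = 0 and n = 200, an effect of 10% of the variance gives:

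| Tested df | Power |
|---|---|
| 1 | 99.7% |
| 5 | 96.7% |
| 10 | 91.1% |
| 15 | 84.8% |
| 19 | 79.9% |

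For a single sleep measure, 80% power is reached at 3.8% of the variance. The 10% is therefore conservative for the model in section 9.3 and matches 80% only for a joint test of about 19 terms, which the plan does not describe.

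**The case against.** The strongest reply is that nothing in the design rests on the 0.1. The operative statement is the 3%, which is correct; the 0.1 is a one-sentence gloss on it, and no analysis uses it. A statistician can recover 0.20 from the preceding sentence. This is fair, and it is why the sample size is not in question. It does not make the sentence harmless: readers who think in correlations will take it at face value.

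It can also be said that the sentence does not repeat the 80%. True, but it presents the correlation as a consequence of the 80%-power effect, so 80% is its natural meaning.

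The 29% sits at the upper end of the 27–29% two-sided range, which should be acknowledged.

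Agreement with the Aim 1 figure of 0.20 is weak support. That figure holds at n = 200 (81% by Fisher z), but section 3.1 frames Aim 1 in older African Americans, planned at 150, where r = 0.20 has about 69% power. The conclusion here does not need the Aim 1 figure.

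Finally, the 10% sentence is not false, since 99.7% power satisfies a claim of 80%. It refers to sleep measures in the plural and may describe a joint test. That stands, and it is why the only defect noted there is the unstated test.

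**Conclusion.** The concern holds. An added 3% of variance over covariates explaining 25% is a partial correlation of 0.20. The stated 0.1 is half that on the correlation scale and a quarter on the variance scale (0.75% against 3%). At n = 200 and the 5% level, power at 0.1 is about 29% two-sided or 41% one-sided.

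The 0.20 follows from the plan's own two inputs alone. The power figures assume one tested degree of freedom and 200 complete participants. They move by only a few points with the number of covariates, the noncentrality convention or n between 190 and 210, and no variant comes near 80%.

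This should be fixed: it misstates the detectable effect for Aims 2 and 3, while leaving the planned sample size sound.

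**What to change.** In section 9.2:

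1. Change the partial correlation from 0.1 to 0.20.
2. Add that power at a partial correlation of 0.10 is about 29% two-sided (27–29% depending on how covariates are counted), so that a null sleep result is not over-read.
3. State whether the 5% test is two-sided.
4. For the closing sentence, either state the test and degrees of freedom behind the 10%, or, if one sleep measure is tested at a time, replace 10% with about 4%.

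The cost is a few words and figures in one section. Sample size, models and significance level are unaffected.
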